## 10. STATISTICAL CONSIDERATIONS

# **10.1.** Sample Size Determination

This study plans to enroll a total of up to approximately 70 patients, including up to 29 patients in Arm A to receive IFX-1 monotherapy and up to 41 patients in Arm B (safety run-in: 9 to 18 patients; Phase II portion: 23 patients) to receive combination therapy with IFX-1 and pembrolizumab.

The 2 treatment arms are evaluated separately. No adjustment for multiplicity will be performed for the application of Simon's 2-stage design in each arm. The sample size of 29 for analyses of the Phase II portion in each treatment arm is based on an optimal Simon's 2-stage design, with 10 patients planned for the first stage and 19 patients planned for the second stage. This sample size is based on a proportion of responders for a drug which is not worth to pursue further of  $p_0=5\%$ . The proportion of responders of a good drug was set to  $p_1=20\%$  for this sample size. The null hypothesis that the best ORR  $p\le0.05$  will be tested versus the alternative hypothesis that p>0.05. This design leads to an expected sample size of about 18 patients per arm and a probability of early termination of 59.9%. If the drug is actually not effective, there is a 4.7% probability of concluding that it is effective (Type I error). If the drug is actually effective, there is a 19.9% probability of concluding that it is not effective (Type II error). After testing the drug on 10 patients in the first stages of both arms, the study will be terminated if no patient responds. If a treatment arm proceeds to the second stage, a total of 29 patients (10 in Stage 1 plus 19 in Stage 2) will be studied for this dose in this treatment arm. If the total number responding is  $\le 3$ , the hypothesis of a potentially effective drug is rejected.

# 10.2. Analysis Sets

For purposes of analysis, the following analysis sets are defined:

Analysis Set	Description
Enrolled Set	All patients who sign the informed consent form
Safety Analysis Set (SAS)	All patients assigned to study treatment and who received
	≥1 dose of study treatment (IFX-1 for monotherapy arm,
	IFX-1 or pembrolizumab for combination arm)
Full Analysis Set (FAS)	All patients assigned to study treatment
Per Protocol Set (PPS)	All patients who received ≥1 dose of study treatment and
	who have ≥1 post-baseline tumor assessment

Protocol violations will be reviewed in the data review meeting. The decisions will be documented in the meeting minutes and finalized before database lock.

In general, safety analyses will be based on the SAS. The primary efficacy analyses will follow an intention-to-treat concept and will be performed on the FAS.

# **10.3.** Statistical Analyses

The statistical analysis plan (SAP) will be developed and finalized before the first patient is enrolled. The SAP will include the exact definition of endpoints and variables to be analyzed, extensive details on the statistical analysis methods to be used together with the structure of tables and figures to be included as end-of-text tables and figures as well as appended listings for the clinical study report. It will also describe procedures for accounting for missing, unused, and spurious data. This section is a summary of the planned statistical analyses of the primary and secondary endpoints.

Individual data will be listed. Data will be summarized using suitable descriptive statistics; depending on the structure of the data, summary statistics (e.g., number of observations, mean, standard deviation, minimum, median, maximum, lower quartile, upper quartile) or frequency tables may be used.

All data will be displayed by treatment arm if not specified otherwise.

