# 3.2.3. Experience in Humans

### 3.2.3.1. IFX-1

IFX-1 is being developed for the treatment of inflammatory diseases. Five clinical studies in humans have been completed so far. One Phase I study in healthy volunteers (Study IFX-1-P1.1) and four Phase II studies; one study in patients with early septic organ dysfunction (Study IFX-1-P2.1), one study in patients undergoing complex cardiac surgery (Study IFX-1-P2.2), and two studies in patients with hidradenitis suppurativa (HS; Study IFX-1-P2.3 and Study IFX-1-P2.4).

As of 01 November 2019, IFX-1 safety had been assessed in approximately subjects. IFX-1 was safe and well tolerated, with no dose relationship in the safety findings. No specific adverse reactions emerged in clinical studies of single or multiple doses IFX-1 in healthy volunteers or patients with cardiac disease, sepsis, or HS.

Currently, four further Phase II studies are ongoing; two studies in patients with granulomatosis with polyangiitis and microscopic polyangiitis (also referred to as antineutrophil cytoplasmic antibody-associated vasculitis; Study IFX-1-P2.5 and IFX-1-P2.6), one study in patients with pyoderma gangrenous (Study IFX-1-P2.7) and one study in severe COVID-19 pneumonia (Study IFX-1-P2.9).

Treatment with IFX-1 was safe and well tolerated with rare occurrence of adverse events (AEs) of special interest (AESIs) that were defined as

. As of December 11, 2019, patients experienced AEs suggestive of . The reactions were moderate, and treatment continued with adequate prophylactic medication. ADAs during treatment were observed in a range of with a trend towards increasing frequency with low dose and larger administration intervals.

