# 5.4. Patient and Study Completion

This study plans to enroll a total of up to approximately 70 patients:

- Arm A (Phase II portion), Stage 1: 10 patients
- Arm A (Phase II portion), Stage 2: 19 patients
- Arm B (safety run-in): 12 to 18 patients (3 to 6 patients per regimen, out of which 6 patients must be treated at MTD or highest dose level)
- Arm B (Phase II portion), Stage 1: additional 4 patients (to reach the required 10 patients on the selected MTD or RP2D)
- Arm B (Phase II portion), Stage 2: 19 patients (to reach the total number of 29 patients on the selected combination dose)

In case none of the patients enrolled in Stage 1 of Arms A or B has a response evaluation of CR/iCR or PR/iPR, enrollment in the treatment arm can individually be stopped. All enrolled patients will be allowed to continue treatment until the end of treatment (EOT) criteria are met (see Sections 5.4.1 and 7.2.4); after the EOT Visit, they will proceed through the planned follow-up period (see Section 5.4.2) until end of study (EOS) (see Section 5.4.3).

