# 7.2.1.2. Combination Therapy Arm B

As detailed in Section 5.1, Stage 1 of treatment Arm B consists of a safety run-in with patients being sequentially assigned to 1 out of 3 different escalating treatment regimens (Figure 3).

IFX-1 will be administered as a 30-minute (-5/+10 minutes) intravenous infusion as follows:

- Cycle 1: 400 mg (regimen 1), 600 mg (regimen 2), or 800 mg (regimen 3) IFX-1 (4 administrations on Days 1, 4, 8, and 15)
- From Cycle 1 Day 22 on:800 mg IFX-1 Q2W (regimen 1), 1200 mg IFX-1 Q2W (regimen 2), or 1600 mg IFX-1 Q2W (regimen 3) until EOT (2 administrations during Cycle 1 on Days 22 and 36 and 3 administrations per cycle on Days 1, 15, and 29 of Cycle 2 and all subsequent cycles)

IFX-1 treatment will be combined with pembrolizumab, starting at Cycle 1 Day 8 and then on Day 1 of each treatment cycle after all other procedures and assessments have been completed. IFX-1 infusion will start 60 minutes (±10 minutes) after the pembrolizumab infusion has been finished.

For those patients receiving less than 1600 mg IFX-1 Q2W (regimen 1 and 2) the dose of IFX-1 may be increased to 1600 mg Q2W at the discretion of the investigator after consultation of the sponsor as soon as the safety of this dose will have been confirmed in at least 3 patients receiving 1600 mg Q2W (regimen 3). This intrapatient dose escalation will only be allowed provided that patient has received at least 2 cycles of IFX-1 and had no Grade  $\geq$  2 treatment related adverse events.

Pembrolizumab will be administered as a 30-minute (-5/+10 minutes) intravenous infusion at a dose of 400 mg Q6W. Sites should make every effort to target infusion timing to be as close to 30 minutes as possible.

The Pharmacy Manual contains specific instructions for the preparation of the pembrolizumab infusion and administration of infusion solution.

Treatment will continue until PD/iCPD or treatment discontinuation for any other reason (see Section 7.2.4) or treatment has been administered for approximately 2 years. If treatment will discontinue due to toxicity, continuation of either IFX-1 or pembrolizumab is allowed, given that the toxicity can be unequivocally attributed to 1 of the drugs (see Section 7.2.4.2).

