#### 10.3.3.1. Pharmacokinetic Analyses

Actual PK sampling date and times will be documented and the plasma concentration of IFX-1 will be assessed by time point. Summary statistics will be provided for the PK concentrations of

IFX-1 at all measured time points including also the geometric mean and its coefficient of variation. PK parameters including but not limited to  $C_{max}$  and  $C_{trough}$ , will be analyzed using descriptive statistics including also the geometric mean and its coefficient of variation.

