#### 10.3.3.2. Immunogenicity Analyses

The number and percentage of patients with detectable ADAs against IFX-1 will be displayed per time point and overall post-baseline.

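### By-arm display of Arm B PK and ADA pools up to three IFX-1 regimens and does not isolate the selected dose; a by-regimen display would be a cheap improvement

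*Combined protocol and SAP*

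**What the plan says.** Section 10.3 states the general rule: "All data will be displayed by treatment arm if not specified otherwise". The two sections on the dose-related secondary endpoints name no other level:

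- Section 10.3.3.1: "Summary statistics will be provided for the PK concentrations of" IFX-1 at all measured time points, with geometric mean and coefficient of variation, and the same statistics for Cmax and Ctrough.
- Section 10.3.3.2: "The number and percentage of patients with detectable ADAs against IFX-1 will be displayed per time point and overall post-baseline".

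Cmax, Ctrough and ADA are Arm B secondary endpoints (4.2.2.2). Section 7.2.1.2 gives the Arm B loading doses as "400 mg (regimen 1), 600 mg (regimen 2), or 800 mg (regimen 3) IFX-1" and the later doses as "800 mg IFX-1 Q2W (regimen 1), 1200 mg IFX-1 Q2W (regimen 2), or 1600 mg IFX-1 Q2W (regimen 3) until EOT". It also lets regimen 1 and 2 patients move to 1600 mg Q2W after at least two cycles, under conditions.

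The one endpoint tied to dose cohort is DLT frequency (4.2.1.2). On ADA in earlier studies, Section 3.2.3.1 reports a "trend towards increasing frequency with low dose and larger administration intervals". The rates are redacted.

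**The concern.** Where dose cohort matters to the authors, as for DLTs, they name it. For PK and ADA they do not, so the default applies and all treated Arm B patients fall into one column.

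The dose rationale in Section 3.2.5.1 rests on a trough threshold, and it presents 1600 mg Q2W as the lowest dose that on average meets the target. By that reasoning the three regimens differ on the very quantity being pooled. A reader who wants the exposure or ADA rate at the dose carried forward would not find it in the planned tables. The pooled geometric mean would be shifted and its coefficient of variation would include the spread between regimens.

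TEAEs raise a narrower issue. Section 4.2.1.2 makes them co-primary for the Phase II portion of Arm B, while Section 10.3.2 analyses the whole safety set, which includes run-in patients on regimens that were not selected.

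**Working it through.** **Plan figures.** Section 10.1 gives "up to 41 patients in Arm B (safety run-in: 9 to 18 patients; Phase II portion: 23 patients". The maximum reproduces: 18 + 23 = 41. Section 5.4 gives "Arm B (safety run-in): 12 to 18 patients (3 to 6 patients per regimen", so its minimum is 12 + 23 = 35. (The run-in minima of 9 and 12 disagree. The counts below follow 5.4.) The chance of stopping at Stage 1 with a true ORR of 5% is 0.95^10 = 0.599, matching the stated 59.9%. At 20% it is 0.80^10 = 0.107. A Stage 1 stop is therefore a realistic case.

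**Inputs.** The dose ratio is 400:600:800 = 800:1200:1600 = 0.5:0.75:1. Each non-selected cohort has 3 to 6 patients (5.4). The selected dose has 29 patients after Stage 2, or 10 if the arm stops at Stage 1 (5.4). Exposure proportional to dose is an assumption. The counts ignore missing samples and any individual dose increase.

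**Formula.** Pooled geometric mean relative to the selected regimen = exp[ Σ nᵢ·ln(doseᵢ / selected dose) / N ].

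Example, 3/3/29: (3·ln 0.5 + 3·ln 0.75)/35 = (−2.079 − 0.863)/35 = −0.084, and exp(−0.084) = 0.919.

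| Selected regimen | n on regimens 1/2/3 | N | Not on selected dose | Ratio |
|---|---|---|---|---|
| 3, Stage 2 done | 3/3/29 | 35 | 17% | 0.919 |
| 3, Stage 2 done | 6/6/29 | 41 | 29% | 0.866 |
| 3, Stage 1 stop | 3/3/10 | 16 | 38% | 0.832 |
| 3, Stage 1 stop | 6/6/10 | 22 | 55% | 0.765 |
| 2, Stage 2 done | 3/29/3 | 35 | 17% | 0.990 |
| 2, Stage 2 done | 6/29/6 | 41 | 29% | 0.983 |
| 1, Stage 2 done | 29/3/0 | 32 | 9% | 1.039 |
| 1, Stage 2 done | 29/6/0 | 35 | 17% | 1.072 |

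For regimen 3, unequal run-in cohorts (3 and 6) stay inside the ranges shown. For regimen 2 they do not cancel as well:
- 6/29/3: exp[(−2.433 + 0.863)/38] = 0.960.
- 3/29/6: exp[(−1.216 + 1.726)/38] = 1.014.

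**Spread.** Geometric CV = √(exp[ln(1 + CV²) + v] − 1), where v is the between-regimen log-variance. With regimen 3 selected, v runs from 0.041 (3/3/29) to 0.082 (6/6/10). The documents give no within-regimen CV. Assumed values of 30%, 40% and 60% would appear as 37% to 43%, 46% to 51% and 65% to 69%.

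**ADA.** The rates are redacted, so this is only an illustration. With an assumed 20% on regimens 1 and 2 and 5% on regimen 3, the pooled rate is (6·0.20 + 29·0.05)/35 = 7.6% for 3/3/29, (12·0.20 + 29·0.05)/41 = 9.4% for 6/6/29, and (12·0.20 + 10·0.05)/22 = 13.2% for 6/6/10.

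**Which dose a sample reflects.** End-of-infusion samples are taken only on Cycle 1 Days 1 and 22 (Schedule of Assessments, PK footnote). That precedes the increase that 7.2.1.2 allows after at least two cycles, so assigned regimen identifies the dose for Cmax. Later troughs and ADA samples may follow a change of dose.

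**The case against.** The strongest reply is that this is silence in a summary. Section 10.3 calls itself a summary and leaves the structure of tables to the SAP. Section 10.3.3 sends PK detail there too. The default gives way to any other specification, individual data will be listed so a split stays possible, and no test or decision depends on these tables. All of this stands, and it limits the weight of the point. It does not remove it: no separate SAP text is in the document reviewed, the only stated rule is by arm, and a listing is not a prespecified summary of a secondary endpoint.

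Three stronger readings are tempting and are not supported.

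- *The pooled values describe no regimen.* If regimen 3 is selected and Stage 2 completes, 29 of 35 to 41 patients (71% to 83%) are on it, and the summary mostly reflects that regimen.
- *TEAE tables are distorted by dose.* Sections 3.2.3.1 and 3.2.5.1 report no dose relationship in safety findings and similar findings across dose groups.
- *A comparison of Arm A with Arm B would show a false pembrolizumab effect on IFX-1 exposure.* No such PK comparison is planned. The descriptive comparison of arms is in the efficacy section (10.3.1).

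The ADA evidence is also limited. The reported trend joins low dose with longer intervals, and the three Arm B regimens share one schedule, so the part due to dose cannot be separated.

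**Conclusion.** The point holds as a cheap improvement. As written, Arm B Cmax, Ctrough and ADA summaries pool up to three regimens over a two-fold dose range and do not isolate the selected dose.

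Under dose proportionality with regimen 3 selected, the pooled geometric mean is 8% to 13% low after Stage 2 and 17% to 23% low after a Stage 1 stop. After Stage 2, it is about 1% to 2% low if regimen 2 is selected with equal cohorts (4% low to 1% high if they are unequal), and about 4% to 7% high if regimen 1 is selected. Three regimens mix only if escalation reaches regimen 3.

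Dose proportionality is an assumption: Section 3.2.5.1 describes a saturable clearance component whose weight is redacted. Any CV is likewise assumed. Increases to 1600 mg Q2W would shrink the gap in later troughs when regimen 3 is the selected dose. No ADA effect size can be derived from the documents, and no dose dependence of TEAEs is claimed.

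**What to change.** In 10.3.3.1 and 10.3.3.2, and in the SAP table structure, state that Arm B PK and ADA are summarised by IFX-1 regimen, with the selected dose as its own column and an all-Arm-B total last.

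- Cmax: by assigned regimen.
- Later Ctrough: by the dose actually given before the sample.
- ADA: by starting regimen, with patients who changed dose flagged.
- TEAEs (10.3.2): add only a column for patients at the selected dose, to match the Phase II scope of the co-primary endpoint.

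Reconcile the run-in minimum (9 in 10.1, 12 in 5.4) so that the expected column sizes are clear.

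The cost is extra table columns, with only 3 to 6 patients in each non-selected run-in column. No sample size, error rate or decision rule changes.

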## 10.3.1. Efficacy Analyses

All efficacy analyses will be performed on the FAS. All analyses will be conducted separately by treatment arm. The 2 treatment arms will be compared descriptively. Patients will be analyzed descriptively and stratified by locally advanced or metastatic cSCC.

The primary efficacy variable is the best ORR (investigator assessed) based on modified RECIST v1.1 criteria (Eisenhauer et al., 2009) and iRECIST criteria (Seymore et al., 2017). The number and percentage of responders will be displayed per treatment arm along with its 95% confidence interval according to Clopper-Pearson.

Patients who discontinue the study after assignment to treatment due to 1 of the following reasons will be counted as non-responder if they have not shown response before discontinuation:

- Lack of efficacy
- AE at least possibly related to study treatment
- PD/iCPD
- Clinical deterioration

Statistical inference will be based on the thresholds defined by the Simon's 2-stage design. For decision criteria at the interim analysis, please refer to Section 10.3.4. At the final analysis, the null hypothesis of an ORR of  $\leq$ 5% will be rejected if >3 patients out of a total of 29 patients respond (CR/iCR/PR/iPR). Due to dropouts, the number of patients evaluable for the primary endpoint might not be exactly 29. In this case, appropriate statistical methods will be applied to correct for the deviation from the planned sample size of 29 evaluable patients (Koyama and Chen, 2008). In this case, appropriate statistical methods will be applied to correct for the deviation from the planned sample size of 29 evaluable patients (Koyama and Chen, 2008). Further details will be specified in the SAP.

Additionally, the number and percentage of patients per RECIST tumor response category will be displayed for each scheduled tumor assessment time point.

Secondary Endpoint	Statistical Analysis Methods
Response (CR/iCR/PR/iPR) duration	Duration of response will be analyzed for patients who reach at least PR/iPR at any time during the study using Kaplan-Meier methods. A responding patient who experiences any form of progression will be evaluated as a patient with event. The starting point is the first diagnosis of CR/iCR or PR/iPR. The time point of the event will be the diagnosis of progression according to RECIST. Responding patients without progression will be censored at their last tumor assessment showing response. Patients who never responded will be excluded from this analysis.
SD duration	Duration of SD will be analyzed using Kaplan-Meier methods. The starting point is the first study treatment administration. A patient who experiences any form of progression will be evaluated as a patient with event. The time point of the event will be the diagnosis of progression according to RECIST (PD) or iRECIST (iCPD). Patients without progression will be censored at their last tumor assessment showing response or any other best overall response except PD/iCPD.
PFS	PFS will be analyzed using Kaplan-Meier methods. A patient who experiences any form of progression or who

	dies of any cause will be evaluated as a patient with event.		
	The time point of the event will be the diagnosis of the		
	first progression according to RECIST/iRECIST or the		
	date of death. Patients without progression and still alive		
	will be censored at their last tumor assessment.		
OS	OS will be analyzed using Kaplan-Meier methods. Death		
	by any cause will be evaluated as event. Patients who are		
	still alive when they discontinue the study will be		
	censored at their last recorded date of being alive.		
Disease control rate	The number and percentage of patients with		
	SD/confirmed SD (iSD) per modified RECIST		
	v1.1/iRECIST or PR/iPR or CR/iCR will be displayed		
	per tumor assessment timepoint.		

Exploratory endpoints will be analyzed descriptively. Further details will be provided in the SAP.

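### Arm B's primary response rate and confidence interval are set on the full analysis set by arm, which mixes the 29 patients planned at the selected dose with 3 to 12 run-in patients on other regimens

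*Combined protocol and SAP*

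**What the plan says.** Section 10.2 defines the FAS as "All patients assigned to study treatment" and adds: "The primary efficacy analyses will follow an intention-to-treat concept and will be performed on the FAS". Section 10.3.1 repeats this: "All efficacy analyses will be performed on the FAS. All analyses will be conducted separately by treatment arm". On the primary variable it says: "The number and percentage of responders will be displayed per treatment arm along with its 95% confidence interval according to Clopper-Pearson". The other three sets (Enrolled, Safety, Per Protocol) are not limited by dose or regimen either. The only stratification named is locally advanced versus metastatic disease.

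Arm B contains three IFX-1 regimens (Section 7.2.1.2). Section 10.1 plans "up to 41 patients in Arm B (safety run-in: 9 to 18 patients; Phase II portion: 23 patients". Section 5.4 gives a different run-in size: "Arm B (safety run-in): 12 to 18 patients (3 to 6 patients per regimen, out of which 6 patients must be treated at MTD".

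The design itself concerns one dose. Section 10.1 says that "a total of 29 patients (10 in Stage 1 plus 19 in Stage 2) will be studied for this dose in this treatment arm". Sections 5.2.2.2 and 10.3.4.2 fill Stage 1 to 10 patients at the recommended Phase II dose (RP2D), and Section 5.4 counts 29 on the selected combination dose. Section 10.3.1 also says: "Due to dropouts, the number of patients evaluable for the primary endpoint might not be exactly 29".

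**The concern.** The decision and the estimate printed beside it would describe different populations. The go/no-go rule is about the selected dose. The ORR and interval, computed as instructed, are about a mixture of regimens.

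The mixture is not fixed in advance. It depends on how many dose-limiting toxicities (DLTs) occur in the run-in, so the same activity at the selected dose gives different headline figures according to the path taken. Some regimen 1 and 2 patients may later move to 1600 mg every two weeks (Section 7.2.1.2), and the plan does not say under which regimen their response is counted.

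**Working it through.** **The plan's own figures.** Section 10.1 gives: stop if 0 of 10 respond, reject if more than 3 of 29 respond, null rate 5%, target rate 20%.

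- Early termination under the null: 0.95^10 = 59.9%.
- Expected size under the null: 10 + (1 − 0.599) × 19 = 17.6.
- Probability of rejection: the sum over x = 1 to 10 of P(X1 = x) × P(X2 > 3 − x), with X1 binomial on 10 and X2 binomial on 19. This gives 4.68% at a 5% rate and 80.11% at 20%, so the type II error is 19.89%.

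All the stated figures reproduce for 10 + 19 patients at one dose.

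**Patients on other regimens.** Each run-in cohort has 3 or 6 patients, and the selected dose is filled to 6. Paths that yield a selected dose (stopping at more than one DLT, Section 7.2.2.2.4) give a run-in of 9, 12, 15 or 18. Subtracting 6 leaves 3, 6, 9 or 12 at other regimens.

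- Three arises only if regimen 1 is selected after regimen 2 stops at three patients.
- With no DLT at all, the number is 6 (3 + 3 + 6 = 12 in the run-in).
- Twelve needs both other cohorts to reach six.
- Under Section 5.4's 12 to 18, the range is 6 to 12.

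**Arm B FAS.** If Stage 2 opens: 23 + (9 to 18) = 32 to 41. If it does not: 10 + (3 to 12) = 13 to 22.

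| Other-regimen patients | Share, Stage 2 opens | Share, stop after Stage 1 |
|---|---|---|
| 3 | 3/32 = 9.4% | 3/13 = 23.1% |
| 6 | 6/35 = 17.1% | 6/16 = 37.5% |
| 12 | 12/41 = 29.3% | 12/22 = 54.5% |

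**Same data, different denominators.** Four responders, all at the selected dose, with Clopper-Pearson 95% intervals:

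| Denominator | ORR | 95% CI |
|---|---|---|
| 29 | 13.8% | 3.9 to 31.7% |
| 35 | 11.4% | 3.2 to 26.7% |
| 41 | 9.8% | 2.7 to 23.1% |

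**Expected pooled ORR.** The formula is (29 × 0.20 + k × q)/(29 + k), where k is the number of other-regimen patients and q their response rate. The documents give no q; I assume 5% to 10%.

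- k = 3: (5.8 + 0.15)/32 = 18.6% to (5.8 + 0.30)/32 = 19.1%
- k = 6: (5.8 + 0.30)/35 = 17.4% to (5.8 + 0.60)/35 = 18.3%
- k = 12: (5.8 + 0.60)/41 = 15.6% to (5.8 + 1.20)/41 = 17.1%

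**Stop after Stage 1.** Suppose none of 10 at the RP2D responds (0%, CI 0 to 30.8%) and one of six other-regimen patients does. The reported primary ORR would be 1/16 = 6.3% (0.2 to 30.2%), beside a decision made on zero responders.

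**Agreement of interval and test.** With responses only at the selected dose, the lower limits are 5/29 5.85%, 5/32 5.28%, 5/35 4.81%, 5/41 4.08% and 6/41 5.57%. Pooling therefore adds a disagreement with the 5% null only at exactly five responders and 35 or more patients. At 4/29 the rule rejects while the two-sided interval (3.9 to 31.7%) includes 5%; that is so with or without pooling.

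**The case against.** The best counter-reading is that the plan already means 29. Section 4.2.1.2 gives the run-in its own primary endpoint (DLT frequency) and places ORR under the Phase II portion. Section 10.1 calls 29 the sample size for analyses of that portion. Section 10.3.1 expects a departure from 29 only through dropouts, whereas a pooled set would depart from 29 by design. On this view the FAS says which assigned patients are kept, the endpoint says which part of the study is measured, and together they give 29. Section 10.3 also calls itself a summary and leaves exact definitions to a separate SAP. Finally, inference rests on the Simon thresholds, so the percentage and interval are only a display.

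Much of this stands as evidence of intent, and the test population is clear. But those passages conflict with the FAS-by-arm rule; they do not override it. The Phase II label does not settle the matter, because Section 10.1 also uses it for 23 enrolled patients (4 + 19), which leaves out the 6 run-in patients at the selected dose. The SAP text is not in the documents. It could add a set, but the protocol itself names the FAS as primary, so an SAP using another set would depart from it.

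It is also fair to say that the size is moderate. With six extra patients the expected ORR falls from 20% to 17.4 to 18.3%, well within the width of the interval at 4/29. The 12-patient case is the extreme, and the 1/16 case is an illustration.

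**Conclusion.** The concern holds for the Arm B ORR estimate and its interval, and only for those. Followed as written, the Arm B FAS includes at least 3 other-regimen patients on every path that yields a selected dose, and 6 on the path with no DLTs. The Stage 1 rule, the test of more than 3 in 29 and the stated error rates are unaffected.

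The denominators and intervals follow from the documents' own counts. The expected pooled ORRs rest on a true 20% at the selected dose and the assumed 5% to 10% elsewhere. This should be fixed, because it concerns the headline figure of a primary endpoint; it does not invalidate the design.

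**What to change.** - In Section 10.2, define an Arm B selected-dose efficacy set: every patient assigned from Day 1 to the regimen finally selected, planned as 6 run-in + 4 Stage 1 + 19 Stage 2 = 29.
- In Section 10.3.1, name this set for the Stage 1 decision, the final test, and the Arm B ORR and interval. Apply the correction already planned there if its size is not 29.
- State how patients assigned but not dosed, or not evaluable, are counted. Section 5.2.2.2 counts patients who received the RP2D, Section 10.3.4.1 counts evaluable patients, and the FAS counts assignment.
- Report run-in patients on other regimens separately by assigned regimen, including any whose IFX-1 dose is later raised.
- Reconcile the run-in size in Section 5.4 (12 to 18) with Section 10.1 (9 to 18).

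The cost is wording in Sections 5.4, 10.1, 10.2 and 10.3.1 and one by-regimen response table. No extra patients or data are needed. The change does not remove the 4/29 disagreement between the rule and the two-sided interval.
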